EXPAREL [®]	Statistical Analysis Plan
EXPAREL®	Statistical Analysis Plan

(Page X of Y)

Protocol: 402-C-319

Listing 16.2-17.5.3.1.1: Adverse Events of Special Interest, as Defined in the Protocol (Group 1: 12 to <17 years) - All Subjects

Treatment: treatment-name

Site	Subject	Preferred Term	Start Time (Day)	End Time (Day)
XXX	УУУУ	Chest Pain Heart Rate Irregular		
XXX	УУУУ			
		•••		

Source: list SAS datasets used to create listing

ddmmmyyyyThh:mm

Note to programmer: Refer to Table 5 for list of AESI's defined in the protocol. Use this template also for listings:

Listing 16.2-17.5.3.1.2: Adverse Events of Special Interest, as Defined in the Protocol (Group 2: 6 to < 12 years) - All Subjects

SAS X.Y

Pacira Pharmaceuticals

(Page X of Y)

Protocol: 402-C-319

Listing 16.2-18.1.1.1: Prior Medications (Group 1: 12 to <17 years) - All Subjects

Treatm	nent: treatment-name		
Site	Subject	Data Type	Date
XXX	УУУУ	Start (Day)	ddmmmyyyyThh:mm (XX)
		Stop (Day)	ddmmmyyyyThh:mm (XX)
		Medication Number	Х
		ATC Level 1	XXXXXXXXXXXXXXXXX
		ATC Level 2	*****
		ATC Level 3	XXXXXXXXXXXXXXXXXXXXXXXXXXXXXXXXXXXXXXX
		ATC Level 4	*****
		Preferred Name	XXXXXXXXXXXXXXXXXXXXXXXXXXXXXXXXXXXXXXX
		Verbatim	*****
		Dose (Unit)	X (XX)
		Route	XXXXXXX
		Frequency	XXXXXXX
		Given for AE or MH?	xxxxxxxxxxxxxxxxx AE # xx (or MH # xx)

ATC=Anatomical therapeutic class Source: list SAS datasets used to create listing

ddmmmyyyyThh:mm

program_name

Note to programmer: If medication is ongoing, put ONGOING in stop row. Do not split a medication across pages. Insert a page break between subjects. Values for category column are: CONCOMITANT; SURGICAL/ANESTHESIA; NON-MEDICATION; PRIOR. For SURGICAL/ANESTHESIA, Frequency is not collected. Use this template also for listings:

Listing 16.2-18.1.1.2: Prior Medications (Group 2: 6 to < 12 years) - All Subjects Listing 16.2-18.2.1.1: Concomitant Medications (Group 1: 12 to <17 years) - All Subjects

Listing 16.2-18.2.1.2: Concomitant Medications (Group 2: 6 to < 12 years) - All Subjects

Treatment:	treatment-name	
Site	Subject	Data Type

Site	Subject	Data Type	Data	
XXX	УУУУ	Start	ddmmmyyyy	
		Stop	ddmmmyyyy	
		System Organ Class	*****	
		Preferred	*****	
		History Verbatim	XXXXXXXXXXXXXXXXXXXXXXXXXXXXXXXXXXXXXXX	
		Start	ddmmmyyyy	
		Stop	ddmmmyyyy	
		System Organ Class	*****	
		Preferred	*****	
		History Verbatim	XXXXXXXXXXXXXXXXXXXXXXXXXXXXXXXXXXXXXXX	
Source: 1	ist SAS dataset	ts used to create listing		ddmmmyyyyThh:mm

SAS X.Y

program name

Note to programmer: Use this template also for the following listing, Replace "TREATMENT" with "SURGERY TYPE", followed by "Spine Surgery" or "Cardiac Surgery".

Listing 16.2-19.1.2: Medical/Surgical History (Group 2: 6 to < 12 years) - All Subjects

Listing 16.2-19.1.1: Medical/Surgical History (Group 1: 12 to <17 years) - All Subjects

Pacira Pharmaceuticals

(Page X of Y)

Protocol: 402-C-319

(Page X of Y)

Protocol: 402-C-319

Listing 16.2-20.1.1: Intraoperative Medications (Group 1: 12 to <17 years) - All Subjects

TREATME	NT: treatment-name	me				
Site	Subject	Medication Name	Dose	Unit	Route	
XXX	УУУУ	XXX	XXX.XX	(UNITS)	XXXX	
XXX	УУУУ	XXX	XXX.XX	(UNITS)	XXXX	

Source: *list SAS datasets used to create table* SAS X.Y

ddmmmyyyyThh:mm

program name

Note to programmer: Use this template also for listing:

Listing 16.2-20.1.2: Intraoperative Medications (Group 2: 6 to < 12 years) - All Subjects

(Page X of Y)

Protocol: 402-C-319

Listing 16.2-21.1.1: Study Drug Administration (Group 1: 12 to <17 years) - All Subjects

TREAT	TREATMENT: treatment-name											
Sito S	Subject	Data	Start Time	Stop Time	Incision Length	Dose	Total Volume					
SILE	Subject	Date			(cm)	(mg)	(mL)					
XXX	УУУУ	ddmmmyyyy	HH:MM	HH:MM	XX.X	XX.X	XXX					

Source:	list	SAS	datasets	used	to	create	table
SAS X.Y							

ddmmmyyyyThh:mm program_name

Note to programmer: Use this template for the following listing. Replace "TREATMENT" with "SURGERY TYPE", followed by "Spine Surgery" or "Cardiac Surgery".

Listing 16.2-21.1.2: Study Drug Administration (Group 2: 6 to < 12 years) - All Subjects

(Page X of Y)

Protocol: 402-C-319

Listing 16.2-22.1.1: Urine Drug Screen, Alcohol Blood Test and Pregnancy Test (Group 1: 12 to <17 years) - All Subjects

TREATM	ENT: treatmen	nt-name				
				Blood		
Site	Subject	Visit	Urine Drug	Alcohol	Pregnancy	
		~ ·				
XXX	УУУУ	Screening	XXXXXXXX	XXXXXXXX	XXXXXXXX	
		Day 1 (Preop)	XXXXXXXX	XXXXXXXX	XXXXXXXX	
		~ ·				
XXX	УУУУ	Screening	XXXXXXXX	XXXXXXXX	XXXXXXXX	
		Day 1 (Preop)	XXXXXXXX	XXXXXXXX	XXXXXXXX	
	***	Screening	\; \; \; \; \; \; \; \; \; \; \; \; \; \	****	***	
XXX	УУУУ	5	XXXXXXXX	XXXXXXXX	XXXXXXXX	
		Day 1 (Preop)	XXXXXXXX	XXXXXXXX	XXXXXXXX	
XXX	УУУУ	Screening	XXXXXXXX	*****	XXXXXXXX	
	ΥΥΥΥ	2				
		Day 1 (Preop)	XXXXXXXX	XXXXXXXX	XXXXXXXX	

Source: list SAS datasets used to create table SAS X.Y

ddmmmyyyyThh:mm program name

Note to programmer: Use this template also for listing:

Listing 16.2-22.1.2: Urine Drug Screen, Alcohol Blood Test and Pregnancy Test (Group 2: 6 to < 12 years) - All Subjects

(Page X of Y)

Protocol: 402-C-319

Listing 16.2-23.1.1: Admission and Discharge (Group 1: 12 to <17 years) - All Subjects

TREATMENT: treatment-name

		Date and Time					
		Surgica	Surgical Facility		ACU		
Site	Subject	Admission	Discharge	Admission	Discharge		
XXX	УУУУ	ddmmmyyyyThh:mm	ddmmmyyyyThh:mm	ddmmmyyyyThh:mm	ddmmmyyyyThh:mm		
XXX	УУУУ	ddmmmyyyyThh:mm	ddmmmyyyyThh:mm	ddmmmyyyyThh:mm	ddmmmyyyyThh:mm		
XXX	уууу	ddmmmyyyyThh:mm	ddmmmyyyyThh:mm	ddmmmyyyyThh:mm	ddmmmyyyyThh:mm		

Source: list SAS datasets used to create table SAS X.Y

ddmmmyyyyThh:mm program name

Note to programmer: Use this template also for listing:

Listing 16.2-23.1.2: Admission and Discharge (Group 2: 6 to < 12 years) - All Subjects

SAS X.Y

402-C-319 Statistical Analysis Plan

Pacira Pharmaceuticals

Listing 16.2-24.1.1: Informed Consent (Group 1: 12 to <17 years) - All Subjects TREATMENT. treatment-name

			Met	Criteria		
		Screening	Signed	Protocol		
Site	Subject	Visit	Consent	Version	Inclusion	Exclusion
XXX	\$7\$7\$7\$7	ddmmmyyyy	ddmmmyyyy	ORIGINAL	YES	YES
XXX	УУУУ УУУУУ	ddmmmyyyy	ddmmmyyyy	AMENDMENT 1	NO	YES
XXX	YYYY	ddmmmyyyy	ddmmmyyyy	ORIGINAL	YES	NO

Source: list SAS datasets used to create table

ddmmmyyyyThh:mm

program name

Note to programmer: Use this template for the following listing. Replace "TREATMENT" with "SURGERY TYPE", followed by "Spine Surgery" or "Cardiac Surgery".

Listing 16.2-24.1.2: Informed Consent (Group 2: 6 to < 12 years) - All Subjects

Protocol: 402-C-319

(Page X of Y)

(Page X of Y)

Protocol: 402-C-319

Listing 16.2-25.1.1: Subject Eligibility (Group 1: 12 to <17 years) - All Subjects

TREATMENT: treatment-name

		Da	ate of	
			Eligibility	
Site	Subject	Informed Consent	Assessment	Criteria Failed
XXX	УУУУ	ddmmmyyyy	ddmmmyyyy	
XXX	УУУУ	ddmmmyyyy	ddmmmyyyy	
XXX	УУУУУ	ddmmmyyyy	ddmmmyyyy	Inclusion: 1, 4
XXX	УУУУ	ddmmmyyyy	ddmmmyyyy	Exclusion: 8, 10, 12

Source: list SAS datasets used to create listing SAS X.Y

ddmmmyyyyThh:mm program name

Note to programmer: Include screen failures in this listing.

Note to programmer: Use this template also for listing:

Listing 16.2-25.1.2: Subject Eligibility (Group 2: 6 to < 12 years) - All Subjects

(Page X of Y)

Protocol: 402-C-319

Listing 16.2-25a: Subject Eligibility Inclusion Criteria - All Subjects

Inclusion Criteria

Xxxxxxxxxxxxxxxxxxxxxxxxx
Xxxxxxxxxxxxxxxxxxxxxxxxx
Xxxxxxxxxxxxxxxxxxxxxxxxx

Source: list SAS datasets used to create listing SAS X.Y

ddmmmyyyyThh:mm program_name

Note to programmer: List inclusion criteria from protocol.

(Page X of Y)

Protocol: 402-C-319

Listing 16.2-25b: Subject Eligibility Exclusion Criteria - All Subjects

E	Exclusion Criteria
Σ	Xxxxxxxxxxxxxxxxxxxxxxx
Σ	Xxxxxxxxxxxxxxxxxxxxxxx
Σ	Xxxxxxxxxxxxxxxxxxxxxxx
Σ	Xxxxxxxxxxxxxxxxxxxxxxxx

Source: list SAS datasets used to create listing SAS X.Y

ddmmmyyyyThh:mm program_name

Note to programmer: List exclusion criteria from protocol.

Pacira Pharmaceuticals, Inc. EXPAREL [®]		402-C-319 Statistical Analysis Plan
Pacira Pharmaceuticals	(Page X of Y)	Protocol: 402-C-319
		11000001. 102 0 515
Listing 16.2-26: Unique Adverse E	vent Terms and Associated Coded Terms	
MedDRA Terms SOC		
Preferred Term	Verbatim(s)	
SOC1	******	
PT1.1	******	

PT1.2	*****	

SOC2		
PT2.1	*****	

Coded using MedDRA

Source: list SAS datasets used to create listing

SAS X.Y

ddmmmyyyyThh:mm program_name

Note to programmer: Sort by SOC and preferred term in alphabetical order.

Pacira Pharmaceuticals, Inc. EXPAREL [®]		402-C-319 Statistical Analysis Plan
Pacira Pharmaceuticals	(Page X of Y)	Protocol: 402-C-319
Listing 16.2-27: Unique Medication	Terms and Associated Coded Terms	
Who Drug Dictionary Terms ACT1 ACT2 ACT3		
ACT4 Preferred name	Verbatim(s)	
ATC1	Verbacim(S)	
ATC1.2		
PN1.2.1	*****	

PN1.2.2	******	
ATC2		
ATC2.2		
ATC2.3		
ATC2.4		
PN2.2.3.4.1	******	

Coded using Who Drug Dictionary		
Source: list SAS datasets used to c	reate listing	ddmmmyyyyThh:mm
SAS X.Y		program_name

Note to programmer: Sort by ATC1, ATC2, ATC3, ATC4 and preferred name in alphabetical order.

IKEAH	MENI. LIE
Site	Subject

EXPAREL[®]

Pacira Pharmaceuticals, Inc.

Pacira Pharmaceuticals

Source: list SAS datasets used to create listing

SAS X.Y

Note to programmer: Subjects may have multiple deviations. Sort deviations by importance, then by treatment, site, and subject. Date may or may not include time. Use this template also for listing: Listing 16.2-28.1.2: Protocol Deviations (Group 2: 6 to < 12 years) - All Subjects

Note to programmer: Replace "TREATMENT" with "SURGERY TYPE", followed by "Spine Surgery" or "Cardiac Surgery".

Protocol: 402-C-319

ddmmmyyyyThh:mm

program name

(Page X of Y)

Listing 16.2-28.1.1: Protocol Deviations (Group 1: 12 to <17 years) - All Subjects

TREATMENT: treatment-name					
Site	Subject	Importance	Date	Description	
XXX	УУУУ	Important Minor	ddmmmyyyyThh:mm ddmmmyyyyThh:mm	xxxxxxxxxxxxxxxxxxxxxxxxxxxxxxxxxxxxxxx	

Protocol: 402-C-319

Pacira Pharmaceuticals (Page X of Y)

Listing 16.2-29-1.1: Physical Exam (Group 1: 12 to <17 years) - All Subjects

TREAT	MENT: treat	ment-name			
			If Not Done, Provid	e	
Site	Subject	Not Done	Reason	Date and Time	
XXX	УУУУ			ddmmmyyyyThh:mm	

Source: list SAS datasets used to create table SAS X.Y

ddmmmyyyyThh:mm program name

Note to programmer: Sort by date and time within subject. Use this template also for listing:

Listing 16.2-29-1.2: Physical Exam (Group 2: 6 to < 12 years) - All Subjects

Figure 1.1.1 Plot of Time to First Rescue Medication Use (Group 1: 12 to <17 years) - Safety Population

[figure not shown]
Note to programmer: Time to first rescue on x-axis 0-72 Hours by 12. Overlay both treatments for Group 1. For table underneath plot, provide for each treatment in Group 1 with a header for treatment. Add footnote: "Subjects who are not administered an opioid rescue medication by 72 hours are censored at 72 hours after surgery or at the time of last follow-up, whichever is earliest."

Use this template for the following figure:

Figure 1.1.2 Plot of Time to First Rescue Medication Use (Group 2: 6 to < 12 years) - Safety Population

Note to programmer: Time to first rescue on x-axis 0-72 Hours by 12. Overlay both surgery types for Group 2. For table underneath plot, provide for each surgery type in Group 2 with a header for surgery type. Add footnote: "Subjects who are not administered an opioid rescue medication by 72 hours are censored at 72 hours after surgery or at the time of last follow-up, whichever is earliest."

Figure 2.1.1 Plot of Mean (± SD) Bupivacaine Concentrations (ng/mL) over Time (Group 1: 12 to <17 years) - PK Population - Linear Scale

Note to programmer: Overlay both treatments for Group 1. For Samples 4-8, use the midpoint of the collection window for the tick mark (i.e. 1.125 for 1-1.25 window). Label the tick mark with the time window (i.e. "1-1.25 hr"). Change the y-axis label to "Bupivacaine Concentration (mg/mL)".

Add footnotes: "For concentrations below the limit of quantification (BLOQ), pre-dose values are set to zero, BLOQ values between the dosing time and the first time point above lower limit of quantification (LLOQ) are set to 0, BLOQ values at time points between two measurable concentration values are set to ½ of LLOQ (lower limit of quantification), and all remaining BLOQ values are set to missing. For Samples 4-8, the midpoint of the collection window is used for the tick mark. "

Use this template for the following figures:

Figure 2.1.2 Plot of Mean (± SD) Bupivacaine Concentrations (ng/mL) over Time (Group 2: 6 to < 12 years) - Spine Surgery - PK Population - Linear Scale

Figure 2.1.3 Plot of Mean (\pm SD) Bupivacaine Concentrations (ng/mL) over Time (Group 2: 6 to < 12 years) - Cardiac Surgery - PK Population - Linear Scale

Figure 2.1.4 Plot of Mean (± SD) Bupivacaine Concentrations (ng/mL) over Time (Both Groups: 6 to < 17 years) - Spine Surgery - PK Population - Linear Scale

[figure not shown]

Figure 3.1.1 Plot of Mean (± SD) Bupivacaine Concentrations (ng/mL) over Time (Group 1: 12 to <17 years) - PK Population - Semi-logarithmic Scale

Note to programmer: Overlay both treatments for Group 1. Change the y-axis label to "Log(Bupivacaine Concentration (mg/mL))". Use this template for the following figure:

[figure not shown]
Figure 3.1.2 Plot of Mean (± SD) Bupivacaine Concentrations (ng/mL) over Time (Group 2: 6 to < 12 years) - Spine Surgery - PK Population - Semi-logarithmic Scale

Figure 3.1.3 Plot of Mean (\pm SD) Bupivacaine Concentrations (ng/mL) over Time (Group 2: 6 to < 12 years) - Cardiac Surgery - PK Population - Semi-logarithmic Scale

Figure 3.1.4 Plot of Mean (± SD) Bupivacaine Concentrations (ng/mL) over Time (Both Groups: 6 to < 17 years) - Spine Surgery - PK Population - Semi-logarithmic Scale

Figure 4.1.1 Plot of Individual Bupivacaine Concentrations (ng/mL) over Time (Group 1: 12 to <17 years) - PK Population - Linear-Linear and Log-Linear

Note to programmer: Modify the figures below as follows: Combine each pair of figures for individual subjects into one figure. Put log-linear scale on right hand side x-axis. Overlay two lines on one figure.

Note to programmer: *Use this template for the following figures:*

Figure 4.1.2 Plot of Individual Bupivacaine Concentrations (ng/mL) over Time (Group 2: 6 to < 12 years) - PK Population - Cardiac Surgery - Linear-Linear and Log-Linear

Figure 4.1.3 Plot of Individual Bupivacaine Concentrations (ng/mL) over Time (Group 2: 6 to < 12 years) - PK Population - Spine Surgery - Linear-Linear and Log-Linear

Figure 4.1.4 Plot of Individual Bupivacaine Concentrations (ng/mL) over Time (Group 1: 12 to <17 years) - PK Population - Linear-Linear and Log-Linear

Note to Programmer: If there is a lot of dose variation (i.e. a lot of departure from 4 mg/kg EXPAREL or Bupivacaine HCl 2 mg/kg), add figures for dose normalized concentration.

Note to programmer: *Use Figure 2.1.1 for the figures below.*

Figure 5.1.1 Plot of Mean (± SD) Numeric Rating Scale at Rest Pain Intensity Scores over Time (Group 1: 12 to <17 years) - Safety Population

Note to programmer: *Replace label on y-axis with "NRS-R". Overlay both treatments for Group 1.*

Figure 5.1.2 Plot of Mean (\pm SD) Color Analog Scale Pain Intensity Scores over Time (Group 2: 6 to < 12 years) - Safety Population

Note to programmer: *Replace label on y-axis with "CAS". Overlay lines for Spine Surgery and Cardiac Surgery for Group 2.*

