5. ANALYSIS POPULATIONS

The Safety Population will consist of all subjects who underwent the planned surgery and received study treatment. All analyses based on the safety population will be by actual treatment received.

The PK Population will consist of subjects who received study drug and provided at least one quantifiable plasma concentration. All analyses will be by actual treatment received.

All analyses of data collected for exploratory purposes (i.e., data related to pain intensity scores and opioid consumption) will be conducted using the safety population, and analyzed according to the actual treatment received.

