6.9.2.1 Time to First Postsurgical Use of Opioid Medication

Time to first postsurgical use of opioid rescue medication will be computed in hours as the date and time of the first opioid rescue medication minus the date and time of the end of surgery. If a subject is not administered an opioid rescue medication, the time to first administration will be censored at 72 hours after surgery or at the time of last follow-up, whichever is earliest. Time to first opioid consumption will be summarized by the quartiles (25th, 50th, and 75th), minimum and maximum estimated using Kaplan-Meier methods within age group and part of the study. The quartile and the 95% confidence limits (CONFTYPE=LOGLOG) for each quartile will be presented.

A Kaplan-Meier plot of the time from end of surgery to first opioid rescue medication use will be presented within age group and part of the study, and a log-rank test p-value of treatment difference shown for group 1.

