ddmmmyyyyThh:mm program_name

(Page X of Y)

Protocol: 402-C-319

Listing 16.2-2.1.1: Randomization and Populations (Group 1: 12 to <17 years) - All Subjects

			Randomization		Population	
Site	Subject	Part	Date and Time	Number	Safety	PK
XXX	VVVV	Part 1	ddmmmyyyyThh:mm	XXXXX	X	x

Part 2

Source: list SAS datasets used to create table SAS X.Y

ddmmmyyyyThh:mm program name

Note to programmer: Population will by 'Y' if subject in set, blank otherwise. Use this template also for listing:

Listing 16.2-2.1.2: Enrollment and Populations (Group 2: 6 to < 12 years) - All Subjects

Note to programmer: Change "Randomization" column header to "Enrollment".

(Page X of Y)

Protocol: 402-C-319

Listing 16.2-3.1.1: Demographics (Group 1: 12 to <17 years) - All Subjects

TREATME	NT: treatme	ent-name						
	Subject							
Site	Number	Init.	Birth Date	Age(yrs)	Sex	Race	Ethnicity	ASA Class
XXX	УУУУ	AMZ	ddmmmyyyy	XX	Х	XXXXXXXXXXX	XXXXXXXXX	Х

The following subjects were not placed in the correct group according to their age: xxxx, xxxx, .

Source: list SAS datasets used to create table

 ${\tt ddmmmyyyyThh:} {\tt mm}$

program name

SAS X.Y

Note to programmer: If race is 'other' then race should be 'Other: other-specify-text'. Use this template also for listing:

Listing 16.2-3.1.2: Demographics (Group 2: 6 to < 12 years) - All Subjects

SAS X.Y

Note to programmer: Use this template also for listing:

Listing 16.2-4.1.2: Height and Weight (Group 2: 6 to < 12 years) - All Subjects

Pacira Pharmaceuticals

Listing 16.2-4.1.1: Height and Weight (Group 1: 12 to <17 years) - All Subjects

Site	Subject	Collection Date	Height (cm)	Weight (kg)	Body Mass Index (kg/m²)
XXX	УУУУ	ddmmmyyyyThh:mm	xxx.X	xxx.X	xx.X

Source: list SAS datasets used to create table

ddmmmyyyyThh:mm

program name

(Page X of Y)

Protocol: 402-C-319

Pacira Pharmaceuticals	(Page X of Y)
------------------------	---------------

Protocol: 402-C-319

Listing 16.2-5.1.1: Surgery (Group 1: 12 to <17 years) - All Subjects

Start Stop Duration Procedure Length Medic	and the state of the second
	cations
Site Subject Date Time Time (hrs) Name (cm) Admini	istered?

Source: list SAS datasets used to create table SAS X.Y

ddmmmyyyyThh:mm program name

Note to programmer: If anesthesia type is 'other' then text should read 'other: specify-text'. Procedure Name is 'Cardiac' or 'Spine'. Use this template also for listing:

Listing 16.2-5.1.2: Surgery (Group 2: 6 to < 12 years) - All Subjects

(Page X of Y)

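### Group 1 pain and opioid outcomes, including the log-rank test, are compared by treatment received rather than by randomised arm

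*SAP*

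**What the plan says.** Protocol section 9.1 makes Group 1 an open-label comparison of EXPAREL with bupivacaine HCl, randomised 1:1, with 15 children per arm in each of two parts. Under sections 11.4.1 and 11.4.2, the assignment comes from a central system once the child is at the site for surgery. The drug is given later, at the end of the operation.

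SAP section 5 defines two populations, Safety and PK. For the first: "The Safety Population will consist of all subjects who underwent the planned surgery and received study treatment". It then says: "All analyses based on the safety population will be by actual treatment received". Its third paragraph extends this to the exploratory pain and opioid data, which "will be conducted using the safety population, and analyzed according to the actual treatment received".

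SAP section 6.9.2.1 plans a Kaplan-Meier plot of time to first opioid, "and a log-rank test p-value of treatment difference shown for group 1". The corresponding mock-up is "Figure 1.1.1 Plot of Time to First Rescue Medication Use (Group 1: 12 to <17 years) - Safety Population", with both treatments overlaid. That title names only the population; the rule on arms is in section 5 and the test is in section 6.9.2.1.

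Neither document plans an as-randomised analysis of these endpoints, even as a sensitivity analysis. Only some rows of the disposition table (Table 14.1-1.1.1) are marked as randomised.

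**The concern.** Counting children by the treatment they received is the usual rule for adverse events and plasma concentrations, which follow from the drug given. A p-value for a treatment difference in time to first opioid is another matter: it can be read as a drug effect only because chance formed the arms. Under the section 5 rule, a child given the other arm's drug moves to the other column, and whatever led to the switch moves too. If that is related to how soon the child would need an opioid, the comparison is biased.

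Group 2 has a single treatment, so Group 1 provides the trial's only randomised comparison of pain and opioid use. SAP section 1 allows planned analyses to appear in study reports, regulatory submissions or manuscripts, so the p-value may be read outside its exploratory setting.

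**Working it through.** **Planned sizes.** The plan's own numbers reproduce: 2 x (15 + 15 + 15) = 90 children; EXPAREL 2 x (15 + 15) = 60; bupivacaine HCl 2 x 15 = 30. Group 1 is 15 v 15 in each part and 30 v 30 over both. The documents give no alpha, power or effect size for the opioid comparison, so there is no such figure to reproduce.

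**Size of the log-rank test.** SAP section 6.9.2.1 works within age group and part, which gives 15 v 15. The titles of Figure 1.1.1 and Table 14.2-4.1.1 name only the group, which could mean 30 v 30. Both sizes are shown.

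**Simulation.** All of the following is assumed and none of it is in the documents:

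- No treatment effect.
- Each child has a prognosis score f drawn from N(0,1).
- Time to first opioid is 6 h x E / exp(f), with E exponential with mean 1, so a high f means an early need.
- Exactly k children (k = 0 to 3) in the comparator arm receive EXPAREL: either the k with the highest f or k chosen at random.

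Times are censored at 72 h, the limit in SAP section 6.9.2.1. The test statistic is z = sum of e(g - p) divided by the square root of the sum of e p(1 - p), where e marks an event, g the arm and p the proportion of children at risk who are in that arm. The test rejects if |z| > 1.96. Each setting has 8,000 trials, and each trial is analysed twice on the same event times, once by arm received and once by arm assigned. With equal arms, no effect and a two-sided test, switching the other way gives the same error rates by symmetry.

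Rejection rates (%):

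| Per arm | Switches | Prognosis-related: as treated | Same trials: as randomised | Random: as treated | Same trials: as randomised |
|---|---|---|---|---|---|
| 15 | 0 | 5.8 | 5.8 | 5.8 | 5.8 |
| 15 | 1 | 6.8 | 6.2 | 6.3 | 6.3 |
| 15 | 2 | 9.2 | 6.0 | 6.2 | 6.1 |
| 15 | 3 | 12.7 | 6.6 | 6.1 | 6.5 |
| 30 | 0 | 5.5 | 5.5 | 5.5 | 5.5 |
| 30 | 1 | 6.4 | 5.7 | 6.3 | 6.2 |
| 30 | 2 | 7.9 | 5.9 | 5.5 | 5.4 |
| 30 | 3 | 9.4 | 5.4 | 5.8 | 5.6 |

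The simulation standard error near 6% is sqrt(0.06 x 0.94 / 8000) = 0.0027, or about 0.3 percentage points.

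**Reading the table.**

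- With no switches the two analyses coincide exactly.
- As randomised, the rate stays at 5.4-6.6% however many children switch. The excess over 5% is small-sample and simulation error.
- As treated, one prognosis-related switch hardly shows, while two or three do, more so at 15 v 15.
- Random switches leave the as-treated rate at 5.5-6.3%, which is no clear inflation.

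**The case against.** The strongest reply is that nothing in the documents plans or predicts a switch. Allocation is central. The only intraoperative rule (Protocol section 10.2) makes a child ineligible for study drug, and section 11.4.3 allows undosed children to be replaced. As written, a difficult operation therefore leads to no dose, not to the other drug. A reader might infer from open-label dosing at the end of surgery that switches in theatre are to be expected and will follow prognosis; the documents do not support that. A dispensing error is equally possible and would bias nothing systematically. Nor should heavy switching be assumed. If 20% of children had difficult operations, an arm of 30 would hold 0.20 x 30 = 6, so a scenario with six switches means every such child is moved, all in one direction.

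Little also rests on the result. The objectives are PK and safety. Protocol section 12.6 calls the pain and opioid endpoints exploratory, section 15.1 rules out formal hypothesis testing, and section 15.7 says significance testing does not apply. Pain scores, pain AUC and opioid totals are only described; the log-rank test is the one between-arm test among these outputs.

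Both arguments stand and limit the size of the point. Neither justifies the rule: SAP section 5 fixes how a switch would be handled, and a between-arm p-value is then attached to the resulting arms.

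A reader might also infer that switches would go unseen, because "Listing 16.2-2.1.1: Randomization and Populations (Group 1: 12 to <17 years) - All Subjects" shows no column for assigned or received treatment. That is unsafe. Mock-up header lines may be incomplete in the public text, and SAP section 6.1 sorts Group 1 listings by treatment. The disposition table, the study drug listing (16.2-21.1.1) and the deviations listing (16.2-28.1.1) could each reveal a switch.

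**Conclusion.** The point holds in conditional form. The plan analyses Group 1 pain and opioid data by treatment received and tests the difference between those arms. Any switch departs from the randomised comparison; only a switch related to prognosis biases it. On the assumptions above, one to three such switches take the nominal 5% log-rank error to about 7-13% at 15 v 15 or about 6-9% at 30 v 30, against about 6% as randomised. These figures illustrate the mechanism and do not forecast this trial, for which no switch rate is given. If no child is switched, nothing changes.

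The consequence is modest: the endpoints are exploratory, one p-value is exposed, and the primary PK objective is unaffected. The correction is still worth making in advance, so that the definition of the arms is not left open to choice once results are known.

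**What to change.** In the third paragraph of SAP section 5, state that Group 1 pain and opioid outputs are analysed by randomised arm: Tables 14.2-1.1.1, 14.2-2.1.1, 14.2-3.1.1 and 14.2-4.1.1, and Figures 1.1.1 and 5.1.1, including the log-rank test. Make the matching exception in the first paragraph of that section, which otherwise applies actual treatment to every analysis on the safety population. Keep actual treatment for safety and PK. List any child whose treatment received differs from the one assigned.

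Children randomised but not dosed stay outside the safety population. The result should therefore be labelled as randomised among treated children, not full intention-to-treat.

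The cost is SAP wording, one treatment variable in the programs and a short listing. No new data are needed, since the disposition table already uses both classifications. The downside is that, if a switch occurs, column Ns in these tables may differ from those in the safety tables, which a footnote can explain.
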